9.2.4 Study discontinuation

Boehringer Ingelheim reserves the right to discontinue the study overall or at a particular study site at any time for the following reasons:

1. Failure to meet expected enrolment goals overall or at a particular study site
2. Emergence of any efficacy/safety information that could significantly affect the continuation of the study, or any other administrative reasons.
3. Violation of Good Clinical Practice (GCP), Good Epidemiological Practice (GEP), or Good Pharmacoepidemiology Practice (GPP) (as applicable), the study protocol, or the contract by a study site or investigator, disturbing the appropriate conduct of the study

The investigator / the study site will be reimbursed for reasonable expenses incurred in case of study termination (except in case of the third reason).

9.3 VARIABLES

9.3.1 Exposures

Currently, 2 anti-fibrotic drugs, namely nintedanib and pirfenidone, have been approved for treating IPF patients. The use of nintedanib and pirfenidone will be according to the Summary of Product characteristics and physician's discretion. Prescription of nintedanib and pirfenidone will be collected and recorded on CRF during the observational period, including start/end date, dose, and the reason for dose adjustment or interruption.

9.3.2 Outcomes

9.3.2.1 Primary outcomes

Key study outcomes are to characterize lung function profile of IPF patients in clinical practice:

- Annual percentage of decline from baseline in FVC
- Annual decline from baseline in DLco
- Annual decline from baseline in resting and exercise SpO₂
- Annual percentage of decline from baseline in TLC
- Annual percentage of decline from baseline in IC

9.3.2.2 Secondary outcomes

- Time to first acute exacerbation of IPF after enrolment
- Annual change from baseline in SGRQ

- Annual change from baseline in CAT
- Annual change from baseline in 6MWT
- Mortality (with cause of death) and time to death

9.3.3 Covariates

Details of handling covariates will be given in the statistical analysis plan (SAP), if any covariates of interest are detected.

9.3.3.1 Baseline characteristics and general information

- Demographics: Age, gender, race, education level, environmental/occupation exposures, height, weight, and BMI.
- Smoking status (current smokers, ex-smokers, or non-smokers)
- Medical history: IPF characteristics regarding diagnosis and comorbidities with related concomitant medications

- IPF characteristics regarding diagnosis:

The procedures used for IPF diagnosis and the results will be documented at enrolment. Data to be collected include performing date, performed method or examination (HRCT, surgical lung biopsy, multidisciplinary team [MDT] diagnosis), and diagnosis results (UIP pattern).

- Comorbidities of interest:

Comorbidities are any medical findings, whether they are present before the start of the study (no retrospective time limit is set) or being an ongoing condition, related data should be collected. For any comorbidity, the status (past or active) should be documented at enrolment. For certain comorbidities the definition are described in the Appendix. Comorbidities included but not limited to diseases listed below are considered to be relevant to IPF:

- i. Cardio and cerebrovascular comorbidities: Arterial hypertension, coronary artery disease (CAD), myocardial infarction (MI), congestive heart failure (CHF), stroke, transient ischemic attack (TIA), peripheral artery disease, atrial fibrillation, deep venous thrombosis, pulmonary embolism, pulmonary hypertension (PH)[#], Anemia, other thromboembolic events, hemorrhage
- ii. Respiratory comorbidities: chronic obstructive pulmonary disease (COPD), emphysema (radiologic), asthma, pneumonia, obstructive sleep apnea

(according to STOP-Bang Scoring Model at baseline)*, respiratory failure, acute exacerbation of IPF

- iii. Renal comorbidities: chronic renal failure
- iv. Hepatic comorbidities: chronic hepatic failure, cirrhosis
- v. Gastrointestinal comorbidities: gastroesophageal reflux disease (GERD), gastric ulcer, GI perforation, inflammatory bowel disease (e.g. Crohn's disease, ulcerative colitis), GI cancer, diverticulitis
- vi. Metabolic comorbidities: T2/T1 diabetes mellitus, hyperlipidemia
- vii. Neoplasms: lung, liver, stomach, colorectal, breast and esophageal, prostate and cervix cancer

#Results of echocardiography will be collected for patients with PH (data collection points: Baseline, Week 28, 52, 76, and 100).

*Data of Berlin questionnaire for obstructive sleep apnea (only collect from patients with suspected/confirmed obstructive sleep apnea according to STOP-Bang Scoring Model) will be collected, including date of assessment and score (data collection points: Baseline, Week 28, 52, 76, and 100).

- Comorbidities related concomitant medications:

Concomitant medications used for treating comorbidities within 6 months prior to enrolment will be collected. Data of interest include start/stop date or ongoing, dose, unit, and frequency.

9.3.3.2 IPF symptoms

Clinical presentations included but not limited to symptoms below are considered to be relevant to IPF. The investigator should assess if patients have the following symptoms and record them on the CRF, at baseline and during each follow-up visits.

- Cough, dyspnea, fatigue, weight loss, dizziness, chest pain, anxiety, aching muscles and joints, clubbed fingers, require oxygen therapy (device), or others (according to physicians' judgment and should be specified on the CRF)

9.3.3.3 Acute exacerbation of IPF

Acute exacerbations of IPF are defined as acute, clinically significant deteriorations of a unidentifiable cause in patients with underlying IPF. Proposed diagnostic criteria were defined as events meeting **ALL** of the following criteria:¹⁰

- Unexplained worsening or development of dyspnea within the previous 30 days
- New diffuse pulmonary infiltrates visualized on chest radiography, HRCT, or both, or the development of parenchymal abnormalities with no pneumothorax or pleural effusion (new ground-glass opacities) since the preceding visit

Non-interventional Study Protocol
BI Study Number 1199-0303**c16462309-02**

Proprietary confidential information © 2017 Boehringer Ingelheim International GmbH or one or more of its affiliated companies

Exclusion of any known causes of acute worsening, including infection, left heart failure, pulmonary embolism, and any identifiable cause of acute lung injury, in accordance with the routine clinical practice and microbiologic studies.

Date of acute exacerbation and corresponding clinical presentations should be recorded on the CRF.

9.3.3.4 Six-minute walk test (6MWT)

Measurement of exercise capacity is an integral element in the assessment of patients with cardiopulmonary disease. 6MWT provides information regarding functional capacity, response to therapy, and prognosis.

It will be assessed if the test was performed and if yes results of 6MWT will be collected at baseline, Week 25, and Week 100. Data of interest include the date of assessment, distance (meter), resting SpO₂ (%), and exercise saturation (SpO₂ %).

9.3.3.5 St. George's Respiratory Questionnaire (SGRQ)

The SGRQ is a 50-item questionnaire developed to measure health status (quality of life) in patients with diseases of airways obstruction. The questionnaire is divided into 3 subscales measuring symptoms (8 items), activity limitation (16 items), and social and emotional impact of disease (26 items). Each item is accorded a weight determined by the degree of distress accorded to each symptom or state described. For each subscale and for the overall questionnaire, scores range from 0 (no effect on quality of life) to a maximum score of 100 (maximum perceived distress); thus, a higher score means a poorer quality of life.¹¹ A minimum change in score of 4 units was established as clinically relevant after patient and clinician testing.¹²

Results of SGRQ will be collected at baseline and every follow-up visit, if available. Data of interest include the date of assessment and SGRQ score.

9.3.3.6 COPD Assessment Test (CAT)

The COPD Assessment Test (CAT) is a simple, 8-item, health status instrument which provides a simple method for assessing the impact of COPD on the patient's health and quality of life. The total CAT score (range of zero to 40) was calculated for each individual by summing the points for each variable. A decrease in CAT score represents an improvement in health status, whereas an increase in CAT score represents a worsening in health status.¹³ The most reliable estimate of the minimum important difference of the CAT is 2 points.¹⁴

Since both COPD and IPF are pulmonary diseases regarding airways obstruction, CAT is used as one of the outcome assessments in this observational study. Results of CAT will be

collected at baseline and every follow-up visit, if available. Data of interest include the date of assessment and CAT score.

9.3.3.7 Mortality

For assessment of mortality, the following data will be collected if death occurs:

- a. Date of death
- b. Cause of death
 - a) Related to IPF
 - i. Respiratory failure:
Is the consequence of lung failure leading to impaired gas exchange; that is, hypoxemia and/or hypercapnia
 - ii. Acute exacerbation of IPF (see definition in Section 9.3.3.3)
 - iii. Other related to IPF (please specify)
 - b) Comorbid condition (please specify):
 - i. Coronary heart disease
 - ii. Cerebrovascular disease
 - iii. Pneumonia/respiratory infection
 - iv. Pulmonary embolism
 - v. Pulmonary hypertension or Pulmonary arterial hypertension/right heart failure
 - vi. Lung cancer
 - c) Other cause (please specify)
 - d) Unknown

9.3.3.8 Serological tests

Since this is an observational study, serological tests will be assessed as judged appropriately by the treating physician according to local medical standards, and the results of interest, including date and results of serological tests with and clinical judgments (normal, abnormal with/without clinical significance) will be collected only if those are available from the medical chart. Results of biomarker tests will be collected at baseline, Week 16, Week 52, Week 76, and Week 100 for the following tests:

- Hematocrit (Hct), hemoglobin (Hb), platelets, RBC, WBC, neutrophils, lymphocytes, monocytes, eosinophils, basophils, C-reactive protein (CRP), creatine kinase (CK), rheumatoid factor, antinuclear antibody, anti-Jo1 antibody, Sjogrens SS-A or SS-B

antibody, scleroderma-70 antibody, cytoplasmic anti-neutrophil cytoplasmic antibody (c-ANCA), and perinuclear anti-neutrophil cytoplasmic antibody (p-ANCA), etc..

9.3.3.9 Biomarker tests

Since this is an observational study, biomarker tests will be assessed as judged appropriately by the treating physician according to local medical standards, and the results of interest, including date and results of biomarker tests, will be collected only if those are available from the medical chart. Results of biomarker tests will be collected at baseline, Week 52, and Week 100 for the following biomarkers:

- PDGF, VEGF, FGF, etc..

9.3.3.10 Gene polymorphism test

Candidate genes help to clarify pivotal aspects in the diagnosis, prognosis, and therapies in IPF. Since this is an observational study, gene tests will be assessed as judged appropriately by the treating physician according to local medical standards, and the results of interest, including date and results of gene tests, will be collected only if those are available from the medical chart. Results of gene tests will be collected at baseline for the following genes:

- Gene is associated with IPF in previous publication: MUC5B,¹⁵ etc..

9.3.4 Study completion

The study will be considered completed for an individual patient when he/she completes 100 weeks of study participation unless reasons for early termination are met (see Section 9.2.2).

The whole study will be completed after estimated 100 patients are enrolled and complete the data collection. Patients who are prematurely withdrawn from the study will not be replaced by an equal number of newly enrolled patients.

A complete end of study visit must be performed for any patient discontinuing study participation. If a patient discontinues the study prematurely, another follow-up assessment should be performed if possible (unless the reason for discontinuation is erroneous enrolment of the patient into the study at baseline). All relevant information, including date, vital status, and the reason for discontinuation, must be recorded on the appropriate page of CRF of the next planned visit.

9.4 DATA SOURCES

As this is a non-interventional study, no diagnostic or monitoring procedures additional to the standard of care and routine practice will be applied to the patients. All the assessment

will be performed by the investigator if they are deemed necessary for the medical treatment procedure.

This non-interventional study will collect the data onto the designed paper case report form (CRF) if available by the investigators or delegated site staffs. Data source includes questionnaires, hospital discharge files, abstracts of primary clinical records, electronic medical records, clinical databases, administrative records such as eligibility files, prescription drug files, biological measurements, exposure/work history record reviews, etc. during the routine clinical practice.

Each patient is identified by a unique central patient identification code, which is only used for study purposes.

9.5 STUDY SIZE

Approximately 100 patients are planned to be enrolled based on the recruitment timeframe and patient pool in 10 medical centers, the expert centers where patients are mainly managed in Taiwan. Since most outcomes are continuous, this number should be sufficient in order to get insights into Taiwanese IPF patients.

9.6 DATA MANAGEMENT

The data from enrolling patients in this study will be recorded on a CRF or other applicable forms. The designated CRO will capture, check, store and analyze the data. The designated CRO will follow Boehringer Ingelheim standard operating procedures (SOPs) and their own internal SOPs.

A data management plan (DMP) will be created to describe all functions, processes, and specifications for data collection, cleaning, and validation.

Data will be transferred to Boehringer Ingelheim after the closure of the study.

9.7 DATA ANALYSIS

Analyses will be performed by a designated CRO. The main analysis population will consist of all eligible patients (i.e. all patients who have signed the informed consent and fulfilled all inclusion criteria and no exclusion criteria).

Analytic specifications, including tables and listings, will be detailed in the statistical analysis plan (SAP) that is separate from the full study protocol and will be updated over time as necessary. A change to the data analysis methods described in the study protocol will require an amendment only if it changes a principal feature of the study objective. Additional exploratory analyses of the data will be conducted as deemed appropriate.

Descriptive analyses will be performed to gain an understanding of the characteristics of the sample studied. Summary statistics of continuous variables will include number, mean,

standard deviation, minimum, Q1 (lower quartile), median, Q2 (upper quartile), maximum value, and 95% confidence intervals, as appropriate.

Tabulations of categorical variables will present all possible categories and display the absolute and relative frequencies. Estimates will be presented with 95% confidence intervals.

Statistical analysis of all data will be performed using the latest version of SAS[®] statistical software (SAS Institute, Cary, NC, USA) or other commercially available standard statistical software.

For analysis of primary and secondary outcomes (spirometry tests, SGRQ, CAT, and 6MWT), imputation will be permitted, if deemed appropriate and on a case-by-case basis, depending on the extent and distribution of missing values, and will be described in the SAP. All information already collected as part of the study will be retained for analysis; however, no further efforts will be made to obtain or record additional information regarding the patient.

9.7.1 Main analysis

The analysis for primary and secondary outcomes, including results of spirometry tests, SGRQ, CAT, and 6MWT will be conducted on the basis of continuous variables, with number, mean (for annual change/decline from baseline, one mean annual change over the whole study period [0-2 years as maximum] will be presented), standard deviation, minimum, Q1 (lower quartile), median, Q2 (upper quartile), maximum value, and 95% confidence intervals included. Wilcoxon Signed Ranked test or t-test, whichever is applicable, will be used to test the change from baseline under a significant level of 0.05.

Time to first acute exacerbation and mortality will be analyzed by Kaplan-Meier estimates, with incidence and time to event included. Time to first acute exacerbation starts from the date of enrolment to the date of first acute exacerbation recorded on the CRF. Patients with exacerbation free at the time of the last contact will be censored. The time of event data will be analyzed using Kaplan-Meier curves. The median, range, and 95% CI for median time and will be reported. Time to death is calculated from the date of enrolment to the date of death from any cause. Patients with no documented death will be censored at the last time they were known to be alive at the time of the last contact. The time of event data (overall survival, censored at 100 weeks) will be analyzed by Kaplan-Meier survival method. The median, range and 95% CI for median survival time and survival curve will be reported.

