9. RESEARCH METHODS

9.1 STUDY DESIGN

This is a non-interventional, multi-center study to collect data from patients with idiopathic pulmonary fibrosis (IPF) in clinical practice in Taiwan. The study will be carried out at 10 medical centers, the expert centers where IPF patients are mainly managed in Taiwan. A total of 100 IPF patients are planned to be included. Only patients who meet all study criteria will be enrolled.

The study duration consists of a 1-year enrolment period and a 2-year follow-up period. IPF patients will be enrolled in a consecutive manner. The observation period was from study inclusion until death, lung transplantation, end of data collection at 2-years, or loss to follow-up. Data collection will be started at the initial screening assessment based on the medical records, and prospectively thereafter if patients are eligible for inclusion.

The study will not interfere with the management of patients by their physician. Visits will be in accordance with clinical needs judged by physicians. All the data will be collected in line with real-world clinical practice (baseline [study enrolment], the first month, and every 3 months afterward).

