10.3 Secondary Endpoints

- Time to first acute exacerbation of IPF after enrolment

Time to first acute exacerbation starts from the date of informed consent to the date of first acute exacerbation recorded on the CRF. Subject with exacerbation free at the time of the last contact will be censored. The time of censored is from the date of consent to the last valid date of last known date subject took anti-fibrotic drugs, date of last contact, and last visit date.

- Annual change from baseline in SGRQ

Descriptive statistics including Number, Mean±SD, Median, Range and 95% C.I. will be presented. Annual change from baseline in SGRQ will be calculated as

$$\text{Annual change from baseline} = \frac{\text{SGRQ}_{\text{follow-up}} - \text{SGRQ}_{\text{baseline}}}{\text{Days of follow-up}} \times 365.25$$

In addition to the annual change from baseline, the mean value and mean change from baseline will also be calculated.

- Annual change from baseline in CAT

Descriptive statistics including Number, Mean±SD, Median, Range and 95% C.I. will be presented. Annual change from baseline in CAT will be calculated as

$$\text{Annual change from baseline} = \frac{\text{CAT}_{\text{follow-up}} - \text{CAT}_{\text{baseline}}}{\text{Days of follow-up}} \times 365.25$$

In addition to the annual change from baseline, the mean value and mean change from baseline will also be calculated.

- Annual change from baseline in 6MWT

Descriptive statistics including Number, Mean±SD, Median, Range and 95% C.I. will be presented. Annual change from baseline in 6MWT will be calculated as

$$\text{Annual change from baseline} = \frac{6\text{MWT}_{\text{follow-up}} - 6\text{MWT}_{\text{baseline}}}{\text{Days of follow-up}} \times 365.25$$

In addition to the annual change from baseline, the mean value and mean change from baseline will also be calculated.

- Mortality (with cause of death) and time to death

Time to death is calculated from the date of consent to the date of death from any cause. Subjects with no documented death will be censored. The time of censored is from the date of consent to the last valid date of last known date subject took anti-fibrotic drugs, date of last contact, and last visit date.

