11.4 Secondary Endpoint Analyses

Time to first acute exacerbation of IPF, and time to death will be analyzed by Kaplan-Meier survival method. The graph of KM curve will be reported and summary statistics including survival estimate (25%, 50%, 75%) and 95% CI for the estimate will be tabulated.

The same analysis procedure of primary endpoints will be applied to the secondary outcomes of annual change, from baseline in SGRQ, CAT and 6MWT. The shapiro-wilk test will be performed to test the normality. Paired t-test will be used if normally distributed. Otherwise, Wilcoxon sign rank test will be adopted to conduct

the test. The sas procedure used for the tests is listed as follow.

Statistical Test	SAS procedures and option
Shapiro-Wilk test	PROC UNIVARIATE NORMALTEST
T-test	PROC UNIVARIATE MU0=0 ALPHA=0.05
Wilcoxon sign rank test	PROC UNIVARIATE MU0=0 ALPHA=0.05

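### Kaplan-Meier for first acute exacerbation censors death and transplantation by default, so it overstates how many patients exacerbate and how early

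*Protocol*

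**What the plan says.** Protocol 9.7.1 sets the method: "Time to first acute exacerbation and mortality will be analyzed by Kaplan-Meier estimates, with incidence and time to event included". It does not define incidence. It gives one censoring rule for this endpoint, "Patients with exacerbation free at the time of the last contact will be censored", and asks for the median with its range and 95% CI.

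SAP 10.3 carries the rule over: "Subject with exacerbation free at the time of the last contact will be censored". The censoring date is taken from the last anti-fibrotic intake, last contact and last visit. SAP 11.4 adds "Time to first acute exacerbation of IPF, and time to death will be analyzed by Kaplan-Meier survival method", with "summary statistics including survival estimate (25%, 50%, 75%) and 95% CI for the estimate will be tabulated". SAP 9 puts all results in two columns, with and without anti-fibrotic drugs.

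Protocol 9.1 defines when follow-up stops: "The observation period was from study inclusion until death, lung transplantation, end of data collection at 2-years, or loss to follow-up". Protocol 9.7.4 refers only to standard survival techniques for incomplete time-to-event data. Neither document mentions competing events, a cumulative incidence function or a composite endpoint.

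**The concern.** A patient who dies or is transplanted without an exacerbation has left observation exacerbation-free, and the only rule that covers this is censoring. Kaplan-Meier treats a censored patient as having the same future risk of exacerbation as those still under observation. That is a reasonable working assumption for loss to follow-up. It fails for a patient who has died, who can no longer exacerbate. The curve then describes a hypothetical population in which nobody dies or is transplanted first.

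First acute exacerbation is a listed secondary outcome, and the primary objective is to describe clinical course in practice. For that aim the natural quantity is the proportion of patients who actually exacerbate. The error runs in one direction and does not shrink with more patients. If mortality differs between the two anti-fibrotic columns, they are distorted by different amounts, and readers will compare them even though no between-group test is planned.

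**Working it through.** The plan states no expected number or rate of exacerbations, so there is no figure to reproduce. The calculation below only sizes the effect.

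**Inputs from the documents**
- Follow-up of 100 weeks (Protocol 9.3.4): t = 700/365.25 = 1.916 years. Week 52: t = 364/365.25 = 0.997 years.
- Median survival of 3 years, and 0.9 year in Taiwan, both from diagnosis (Protocol 7). With a constant hazard these give ln2/3 = 0.231 and ln2/0.9 = 0.770 per year.
- About 100 patients (Protocol 9.5).

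**Assumptions**
- Constant hazards.
- Exacerbation hazard h1 = 0.05, 0.10 or 0.20 per year.
- Hazard of exacerbation-free death h2 = 50% or 100% of the death hazard. The 50% case allows for fatal exacerbations, which count as events when recorded.
- Transplantation is left out because no rate is given; it would add to h2.

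**Formulas**
- One minus Kaplan-Meier, deaths censored: 1 − exp(−h1·t)
- Cumulative incidence, death competing: h1/(h1+h2) × [1 − exp(−(h1+h2)·t)]

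**Worked case** (h1 = 0.10, 3-year median, 100% share, Week 100)
- One minus Kaplan-Meier: 1 − exp(−0.1916) = 17.4%
- Cumulative incidence: 0.10/0.331 × [1 − exp(−0.331 × 1.916)] = 0.302 × 0.470 = 14.2%
- Ratio: 1.23

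**Week 100, all cases**

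| h1 per year | 1 − KM | Cumulative incidence, 3-year median (50% / 100% share) | Cumulative incidence, 0.9-year median (50% / 100% share) |
|---|---|---|---|
| 0.05 | 9.1% | 8.2% / 7.4% | 6.5% / 4.8% |
| 0.10 | 17.4% | 15.7% / 14.2% | 12.5% / 9.3% |
| 0.20 | 31.8% | 28.8% / 26.1% | 23.0% / 17.4% |

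- Ratios at Week 100: 1.11–1.23 (3-year) and 1.38–1.89 (0.9-year). At Week 52: 1.06–1.12 and 1.20–1.43.
- Exacerbation-free deaths per 100 patients by Week 100, h2/(h1+h2) × [1 − exp(−(h1+h2)·t)]: 17–34 (3-year) and 44–74 (0.9-year).
- Sampling error at n = 100 in the 3-year cases, 1.96 × √[CIF(1 − CIF)/100]: about 5–9 points, against an excess of 0.9–5.8 points.
- In simulated cohorts of 100 patients, the mean Kaplan-Meier and Aalen-Johansen values agree with the formulas to within 0.2 points.

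**Quantiles**
- At h1 = 0.20, Kaplan-Meier reaches 25% at −ln(0.75)/0.20 = 1.44 years (Week 75).
- The cumulative incidence reaches 25% at 1.59–1.80 years (Weeks 83–94) with the 3-year median.
- With the 0.9-year median it does so at 2.25 years (50% share, after follow-up ends) or never (100% share, plateau 20.6%).
- At h1 = 0.05 and 0.10, Kaplan-Meier reaches 25% only at 5.75 and 2.88 years, beyond follow-up. For all three rates the median lies beyond Week 100 by either method.

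**Subgroup columns**

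Take h1 = 0.10 and a 50% share in both columns, with a 3-year median in one and a 0.9-year median in the other. Kaplan-Meier shows 17.4% in both, while the cumulative incidences are 15.7% and 12.5%.

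**The case against.** The strongest reply is that the SAP plans a curve and quantiles, not landmark probabilities at Weeks 52 and 100. Incidence appears once in Protocol 9.7.1 and could mean a crude count over N, which Kaplan-Meier does not inflate. That stands for the crude count, but the curve and its quantiles remain affected.

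At the two lower assumed rates no quantile is reached within 100 weeks, so none can be distorted. That stands too; the quantile effect appears only at 0.20 per year.

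The rates and the 50% floor are assumptions. Acute exacerbation is itself a listed cause of death (Protocol 9.3.3.7), so the competing share could be lower. At 25% of the death hazard with the 3-year median, the Week 100 excess is only 0.5, 0.9 and 1.6 points (ratio about 1.05) against half-widths of 5.5–9.0 points. The 0.9-year median comes from the 1997–2007 Taiwan source, before anti-fibrotics were marketed there, and the contrast between subgroup columns is hypothetical. All this limits the likely size but cannot reverse the direction.

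Finally, Kaplan-Meier with death censored is a legitimate cause-specific description, and deaths are reported separately. That is so, but nothing in the plan labels the curve that way, and the protocol attaches incidence to it.

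**Conclusion.** The concern holds. Censoring at death and transplantation is inferred from the general rule, since no sentence states it, but no other rule is available. Whenever such an event precedes a first exacerbation, one minus Kaplan-Meier is at or above the proportion who exacerbate, and its quantiles are at or before the true ones. That conclusion needs no assumed rate.

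The size does. Under the 3-year median the bias is moderate and below sampling error; under the 0.9-year median it could approach a doubling. The constant hazards, the exacerbation rates and the competing share are assumptions, and both medians run from diagnosis rather than enrolment. The plan should be changed because the error is systematic and cheap to remove. It does not invalidate the study, and Kaplan-Meier for overall survival is unaffected.

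**What to change.** In SAP 10.3 and 11.4, and in Protocol 9.7.1 when next revised:

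- Define the incidence of first acute exacerbation as the Aalen-Johansen cumulative incidence, with death without exacerbation and lung transplantation as competing events.
- Report it with 95% CIs at Weeks 52 and 100, overall and in each anti-fibrotic column.
- If the Kaplan-Meier curve is kept for this endpoint, label it cause-specific with death and transplantation censored, and do not read it or its quantiles as incidence.
- Keep Kaplan-Meier for overall survival, and record the change in SAP 12.

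The cost is a SAP update and a little programming. No new data are needed. Protocol 9.3.4 already requires: "All relevant information, including date, vital status, and the reason for discontinuation, must be recorded on the appropriate page of CRF". The discontinuation reasons in Protocol 9.2.2 include death and transplantation. A protocol amendment should not be needed either. Protocol 9.7 sets the threshold: "A change to the data analysis methods described in the study protocol will require an amendment only if it changes a principal feature". That test concerns what the study aims to show, which this change leaves as it is.
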